#### 8.2.4. Modified Rankin Scale

The mRS is a global disability scale that measures the overall independence of stroke patients. The level of disability following a stroke is assessed via a 7-point scale (0-6), where 0 is no limitation or symptom and 6 is death. It is expected that all subjects will have a baseline of 1 (no significant disabilities despite symptoms) up to 5 (severe disability, bedridden, incontinent, and requiring constant nursing care and attention).

[REDACTED]

[REDACTED]

For each shift table, missing values will not be included, so the denominator for percentages will be the number of subjects with a mRS score at both Baseline and the visit. No missing values will be imputed and no statistical inference will be performed on the shift tables.

The frequency and percentage of subjects with each grade on the mRS [REDACTED] will be presented by treatment group.

The frequency and percentage of subjects who achieve a score of 0-2 on the mRS [REDACTED] will be presented by treatment group. Comparisons by treatment group will be made [REDACTED]. No formal adjustment for multiple comparisons will be made.

[figure not shown]
The proportion of subjects with an increase in the mRS of  $\geq 3$  points, increase of 2 points, increase of 1 point, no increase/decrease, decrease of 1 point, decrease of 2 points and decrease  $\geq 3$  points from Baseline will be presented by treatment group [REDACTED]

[REDACTED]. No formal adjustment for multiple comparisons will be made.

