APPENDIX 3.

Modified Rankin Scale (Sample)

Score	Description
0	No symptoms at all
1	No significant disability despite symptoms; able to carry out all usual duties and activities
2	Slight disability; unable to carry out all previous activities, but able to look after own affairs without assistance
3	Moderate disability; requiring some help, but able to walk without assistance
4	Moderately severe disability; unable to walk without assistance and unable to attend to own bodily needs without assistance
5	Severe disability; bedridden, incontinent and requiring constant nursing care and attention
6	Dead

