### **6.3. Missing Data**

Missing data will not be estimated and/or imputed in any way. Adverse events(AEs) with missing onset dates will be included as treatment-emergent.

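### In the SAP's mRS change table, a death scored 6 from baseline grade 4 or 5 cannot reach the worst row, while some non-fatal worsening does

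*SAP*

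**What the plan says.** SAP 8.2.4 describes the mRS as "assessed via a 7-point scale (0-6), where 0 is no limitation or symptom and 6 is death". Protocol Appendix 3 has the same top end: grade 6 is death, and grade 5 is "Severe disability; bedridden, incontinent and requiring constant nursing care and attention". On the starting point, the SAP states: "It is expected that all subjects will have a baseline of 1 (no significant disabilities despite symptoms) up to 5".

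The section then plans a table of change in seven rows: a rise of 3 or more, then "increase of 2 points, increase of 1 point, no increase/decrease, decrease of 1 point, decrease of 2 points", then a fall of 3 or more. These are "points from Baseline will be presented by treatment group", and a sentence follows saying that multiple comparisons will not be adjusted for. Part of the text after the category list is redacted. The visible text gives death no row of its own and has no rule for placing it. The visible mRS section of the protocol (14.4.4) does not contain this table.

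The same SAP section also plans the frequency of every mRS grade by arm, and shift tables for subjects scored at both Baseline and the visit. SAP 10.12 and 10.13 report bleeding-related and all-cause mortality by arm. On missing values, SAP 6.3 states: "Missing data will not be estimated and/or imputed in any way".

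**The concern.** Grade 6 is the top of the scale, so the largest rise a subject can show is 6 minus the baseline grade. The more disabled the subject is at entry, the smaller the rise that death can produce. Someone reading down the rows would take them as running from worst to best. For deaths from the two most disabled baseline grades that reading fails: they share rows with modest non-fatal worsening, while some survivors sit in the row above them.

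What is at stake is one planned by-arm summary in a study whose primary objective is safety. Read alone, it would understate the worst outcome for subjects who entered with grade 4 or 5.

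**Working it through.** **Inputs.** Death = 6 and expected baseline = 1 to 5 (SAP 8.2.4). Rows = the seven change categories (SAP 8.2.4). Sample size = 24, allocated 2:1 (SAP 3.5). The documents give no figure for this table, so there is nothing to reproduce first.

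**Step 1: where a death falls.** Change = 6 − baseline.

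| Baseline grade | Change at death | Row |
|---|---|---|
| 1 | 6 − 1 = 5 | rise of 3 or more |
| 2 | 6 − 2 = 4 | rise of 3 or more |
| 3 | 6 − 3 = 3 | rise of 3 or more |
| 4 | 6 − 4 = 2 | rise of 2 |
| 5 | 6 − 5 = 1 | rise of 1 |

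No outcome from grade 4 or 5 reaches the worst row.

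**Step 2: what shares each row.** All pairs of baseline 1 to 5 and follow-up 0 to 6 were enumerated.

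- Rise of 1: 1→2, 2→3, 3→4, 4→5 and the death 5→6.
- Rise of 2: 1→3, 2→4, 3→5 and the death 4→6.
- Rise of 3 or more: the non-fatal moves 1→4, 1→5 and 2→5, and the deaths 1→6, 2→6 and 3→6.

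So three non-fatal moves are placed above two kinds of death.

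**Step 3: weight of one death.** 24 × 2/3 = 16 on LT3001 and 24 × 1/3 = 8 on placebo. If every subject is scored, one death is 1/16 = 6.25 percentage points or 1/8 = 12.5 percentage points of its arm.

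**Step 4: the parallel NIHSS table.** SAP 8.2.3 gives death an NIHSS of 42, SAP 3.4.1 admits scores of 4 to 30, and the worst row in SAP 10.14 is a rise of 4 or more. If death is scored 42 and baseline is within the eligible range, the smallest rise at death is 42 − 30 = 12, so every death lands in the worst row. The ceiling problem belongs to the mRS table.

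**Step 5: share of deaths that would miss the worst mRS row.** This needs a baseline distribution p and a relative death risk r by grade, which the documents do not give. Share = (p₄r₄ + p₅r₅) / Σ pᵢrᵢ. Under assumed inputs:

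| Assumed baseline mix, grades 1 to 5 (%) | Assumed relative risk | Share missing the worst row |
|---|---|---|
| 30/30/20/15/5 | equal | 20% |
| 20 each | equal | 40% |
| 30/30/20/15/5 | doubling per grade | 2.0/3.7 = 54% |
| 20 each | proportional to grade | 9/15 = 60% |
| 5/10/20/40/25 | equal | 65% |
| 20 each | doubling per grade | 24/31 = 77% |
| 5/10/20/40/25 | doubling per grade | 7.2/8.25 = 87% |

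The range of 20% to 87% reflects the assumptions, not trial data. Steps 1 and 2 need no distribution or risk.

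**Step 6: whether a death is scored at all.** Steps 1 to 3 presume that 6 is entered at each visit after death. No visible sentence says so. Under SAP 6.3, a visit with no recorded score could be treated as missing, and the subject would leave the table. A death from grade 4 or 5 is then either shown as a rise of 1 or 2 points or not shown.

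**The case against.** The strongest reply is that no death would be overlooked. All-cause mortality is a listed secondary endpoint with its own by-arm comparison, and bleeding mortality is reported separately. The grade frequencies show grade 6, and a shift table shows a 5→6 or 4→6 move directly. This stands, and it limits the point to one table. The grade and shift tables do depend on the same unstated scoring of deaths; the mortality analyses do not.

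It is also true that the change categories are not among the mRS endpoints in SAP 4.2, that a move from 5 to 6 is arithmetically one point, and that a baseline-5 survivor's inability to worsen is a property of the scale. None of this gives the rows a sensible order when deaths are mixed in.

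Redaction matters too. A rule for deaths could sit in the blacked-out text of SAP 8.2.4 or section 12, or in the separate table shells. The point rests on the visible text only.

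Three stronger readings are tempting, and the documents do not support them:

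- A reader might infer that the likeliest deaths are the ones misplaced. There is no death risk by baseline grade and no baseline mRS distribution to show this; Step 5 only shows how far the answer moves with the assumptions.
- A reader might infer that the plan could conceal a mortality signal. The separate mortality analyses rule that out.
- A reader might infer from the multiplicity sentence that an ordered test is planned on these rows. Any method is redacted, so this cannot be established.

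**Conclusion.** The point holds as a defect of ordering in one supplementary table. On the visible text, deaths scored 6 from baseline grades 4 and 5, two of the five expected grades, cannot enter the worst row, while the survivor moves 1→4, 1→5 and 2→5 do. Each such death is 6.25 percentage points of the LT3001 arm or 12.5 of the placebo arm.

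This rests on two assumptions: deaths are entered as 6 at the visit, and no redacted sentence already gives them a place. It does not rest on which subjects are more likely to die. No listed endpoint or mortality result is affected. The change is worth making because it is nearly free and because the treatment of deaths at later visits needs stating in any case.

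**What to change.** In SAP 8.2.4 and the matching table shell:

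1. Add a separate row, *Died (mRS 6)*, to the change table. Count every death there whatever the baseline grade, so that the point-change rows contain survivors only.
2. If the rows are compared in order, treat that row as the worst category, beyond a rise of 3 or more.
3. State that a subject who has died counts as mRS 6 at later visits and is not dropped as missing, so that the no-imputation rule in SAP 6.3 is not read as excluding deaths.

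If the redacted text or the shells already hold such a rule, checking that it agrees with these three statements is enough.

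The cost is a short SAP insertion and one table row, using data already collected. The downside is one more sparse row in a 24-subject table.

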**Statistical Analysis Plan**

Sponsor: Lumosa Therapeutics Co, Ltd; Protocol No.: LT3001-201

---

[figure not shown]

This document is confidential.

**Statistical Analysis Plan**

Sponsor: Lumosa Therapeutics Co, Ltd; Protocol No.: LT3001-201

---

This document is confidential.

SAP Version: 2.0, 23-Mar-2021

[figure not shown]
Filing requirements: TMF

Page 25 of 47

**Statistical Analysis Plan**

Sponsor: Lumosa Therapeutics Co, Ltd; Protocol No.: LT3001-201

---

This document is confidential.

SAP Version: 2.0, 23-Mar-2021

[figure not shown]
Filing requirements: TMF

Page 26 of 47

**Statistical Analysis Plan**

Sponsor: Lumosa Therapeutics Co, Ltd; Protocol No.: LT3001-201

---

This document is confidential.

SAP Version: 2.0, 23-Mar-2021

Filing requirements: TMF

Page 27 of 47

## **10. Safety**

### **10.1. Extent of Exposure**

This is a single-dose study. A listing will be provided for IP administration.

### **10.2. Treatment Compliance**

Not applicable to this study.

### **10.3. Adverse Events / Adverse Drug Reactions**

An AE is any symptom, physical sign, syndrome, or disease that either emerges during the study or, if present at Screening [REDACTED] worsens during the study, regardless of the suspected cause of the event.

Treatment-emergent AEs (TEAEs) are defined as events with onset dates on or after the start of the IP. AEs with missing onset dates will also be included as TEAEs.

AE will be coded with Medical Dictionary for Regulatory Activities (MedDRA) in place at the time of analysis and grouped by SOC and PT.

An SAE is any untoward medical occurrence, in the view of either the Investigator or Sponsor, that:

- results in death
- is life-threatening
- results in inpatient hospitalization or prolongation of existing hospitalization
- results in persistent or significant disability/incapacity, and/or
- is a congenital anomaly/birth defect

Other important medical events that may not be immediately life-threatening or result in death or hospitalization, based upon appropriate medical judgment, are considered SAEs if they are thought to jeopardize the subject and/or require medical or surgical intervention to prevent one of the outcomes defining an SAE.

All AEs will be included in data listings and listed by subject, along with information regarding onset, duration, relationship and severity to investigational product, action taken with investigational product, treatment of event, and outcome.

Drug-related AEs are defined as AEs with possible, probable, or definite relationship to study drug.

AEs are classified as mild, moderate and severe in intensity-

All AE summaries will be restricted to TEAEs only.

The number and percentage of subjects as well as number of events will be presented for TEAE summaries. For summaries by SOC, PT, and maximum intensity, a subject will be counted once at the highest intensity for which the event occurred at the SOC level and the highest intensity for each unique PT within that SOC level. Summaries by relationship to study drug will be handled similar to the summaries by intensity.

The following summaries will be provided.

This document is confidential.

- Overall summary of TEAEs by treatment group and overall
- TEAEs within 90 days by SOC and PT
- TEAEs within 90 days by SOC, PT and maximum intensity
- TEAEs within 90 days by SOC, PT and maximum relationship to study drug
- Drug-related TEAEs within 90 days by SOC and PT
- Serious TEAEs by SOC and PT
- TEAEs leading to study discontinuation by SOC and PT

[figure not shown]
All AEs will be listed with TEAE identified.

#### **10.4.        Laboratory Evaluations**

Laboratory data including hematology, coagulation/clotting and clinical biochemistry will be summarized descriptively at each time point, [REDACTED]

[REDACTED] by treatment, using mean values and mean change from baseline values, as well as numbers of subjects with values outside limits of the normal range. [REDACTED]  
[REDACTED]

Subject listing of laboratory tests will be provided. Abnormal laboratory values will be flagged and will be identified in the listings. The abnormal laboratory values will also be presented in the listings.

This document is confidential.

## 10.5. Vital Signs

Vital signs includes body temperature (°C), pulse rate (beats/min), respiration rate (breaths rate/min), systolic and diastolic blood pressure (mmHg). Body temperature (°C) and respiration rate (breaths rate/min) will be collected [REDACTED]

[REDACTED]. Pulse rate (beats/min) and systolic and diastolic blood pressure (mmHg) will be collected at Screening (Visit 1), Visit 2 (Day 0), Visit 2-PK (5 min, 10 min, 15 min, 30 min and 1 hours after dosing), Visit 3 (24 Hours), on Visit 4 (Day 7), Visit 5 (Day 30) and at ET.

Vital signs will be summarized at each time point by treatment, using mean values and mean change from baseline values, as well as numbers of subjects with values outside limits of the normal range. Shift table (normal, abnormal NCS, abnormal CS) will also be provided at each time point by treatment.

Subject listing of vital signs will be provided. Subjects with abnormal vital signs interpretation will be presented in the listings.

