5.2.1 Nonclinical Studies

The nonclinical program for LT3001 included the following:

- In vitro pharmacology studies to evaluate antioxidant activity, anti-platelet activity, [REDACTED] and binding to receptors and critical enzymes;
- In vivo pharmacology studies to evaluate efficacy in mouse, rat, and monkey models of stroke;
- Good Laboratory Practices (GLP) safety pharmacology studies, involving neurological and respiratory in rats, cardiovascular in dogs, an in vitro human Ether-a-go-go Related Gene (hERG) assay, and a non-GLP cardiovascular study in monkeys;
- In vivo pharmacokinetic (PK)/toxicokinetic evaluations in rats, dogs, and mini-pigs;
- In vitro distribution and metabolism studies using mouse, rat, dog, monkey, mini-pig, and human hepatocytes;
- Acute toxicity studies in rats, dogs, monkeys, and mini-pigs;
- 14-day repeat-dose GLP toxicity studies in rats and dogs;
- 6-day repeat-dose GLP toxicity study in mini-pigs;
- In vitro genotoxicity studies and in vivo genotoxicity evaluation in rats; and
- In vitro phototoxicity study.

A summary of noteworthy findings from these nonclinical studies is listed below:

- Effect of LT3001 on the bleeding time was evaluated in male ICR mice and was comparable to animals that received vehicle control and significantly shorter than those treated with rtPA (10 mg/kg).
- LT3001 showed stronger antioxidant capacity than the known antioxidant control substances (Trolox®, L-ascorbic acid, and Edaravone).
- The interaction of LT3001 and Aspirin was assessed by optical microplate-based assay. LT3001 [REDACTED] showed no effect on Aspirin's anti-platelet aggregation activity.
- In secondary pharmacodynamic studies, LT3001, [REDACTED] had no effect on any of the receptors or critical enzymes evaluated.
- In GLP safety pharmacology studies in vivo, LT3001 [REDACTED] showed no biologically significant effect in either the central nervous system Irwin test or respiratory physiological parameters in rats.
- In a GLP [REDACTED] assay in vitro, [REDACTED] inhibition of mean hERG-mediated potassium currents was observed at the highest concentration tested [REDACTED] No inhibition was observed [REDACTED].
- In 2 GLP cardiovascular studies in dogs, a decrease in blood pressure and an increase in heart rate (with concomitant decreases in RR, PR, and uncorrected QT intervals) were observed at LT3001 [REDACTED]

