- In a non-GLP cardiovascular study in monkeys, a decrease in blood pressure and an increase in heart rate (a compensatory response to decreased blood pressure) were observed [REDACTED]. The effects on cardiovascular parameters were all transient and recovered to normal range within a few hours.
- PK studies of LT3001 in rats, dogs, and mini-pigs indicated that LT3001 plasma levels increased roughly in proportion to the IV dose [REDACTED] with no signs of accumulation after repeated doses.
- In vitro protein binding studies showed that LT3001 does not bind significantly to human serum albumin (HSA) or serum acid alpha-1-glycoprotein (AGP), which are considered the most relevant drug carriers in human plasma. [REDACTED]
- In vitro metabolite identification studies with LT3001 were conducted using plasma and following in vitro incubation with hepatocytes from mice, rats, dogs, monkeys, mini-pigs, and humans. [REDACTED]

- LT3001 was not phototoxic and showed no genotoxic activity in either the Ames test or the chromosomal aberration assay with Chinese Hamster Ovary (CHO) cells. LT3001 did not induce micronuclei in rat bone marrow cells.
- Acute toxicity studies with LT3001 were conducted in rats, dogs, monkeys, and mini-pigs, respectively. [REDACTED]

- The repeat-dose toxicity of LT3001 was evaluated in a 5-day non-GLP study in dogs [REDACTED] 14-day GLP repeat-dose (once daily) IV toxicity studies in rats [REDACTED] and in dogs [REDACTED] and a GLP repeat-dose [REDACTED] study in Bama mini-pigs [REDACTED]. Notable LT3001-related findings included swelling and discoloration at the injection site on the tail and mild vocalization during dosing in rats; and prolonged capillary refill time, weak pulse, rapid respiration, recumbency, decreased activity, and skin redness in dogs. These clinical signs subsided or became absent with subsequent dosing. There was no mortality reported in either of the 14-day studies or during the dosing period in the 6-day mini-pig study ([REDACTED] prior to scheduled Day 14 sacrifice, due to a moribund condition). The no observed adverse effect levels (NOAELs) were determined [REDACTED]

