## **6. General Aspects for Statistical Analysis**

### **6.1. General Methods**

- The statistical evaluation will be performed using SAS® software version 9.4 or higher (SAS Institute, Cary, NC). All data will be listed, and summary tables will be provided.
- Summary statistics will be presented by treatment group and overall. For continuous variables, data will be summarized with the number of subjects (N), mean, standard deviation (SD), median, minimum, and maximum by treatment group. For categorical variables, data will be tabulated with the number and proportion of subjects for each category by treatment group.
- The dictionary (MedDRA and WHODrug) version used will be specified in corresponding data display footnote.
- Unless otherwise stated, all listings will include all subjects in ITT Population, and all listings will be sorted by subject ID, treatment, and assessment date/time.
- For all percentage calculations, the denominator will be the number of subjects in the relevant population, unless otherwise stated.
- Only data from protocol scheduled visits will be included in the summary tables. Data from unscheduled visits will not be included in the summary tables but will be included in the listings.

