### **6.2. Key Definitions**

- Baseline Value: unless otherwise defined, the last non-missing assessment prior to first dosing will serve as baseline value.

Unknown, Not Done, Not Applicable and other classifications of missing data will not be considered when calculating baseline observations. However, valid categorical observations will be considered for baseline calculations.

- Study day: number of days since the study drug administration. Study day is calculated using the formula: Study day = date of assessment - date of first dosing

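### SAP 10.5 counts out-of-range vital signs without direction, so if baseline pressure is raised, the count and the shift table can show a drug-caused blood pressure fall as improvement

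*SAP*

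**What the plan says.** SAP 10.5 (Vital Signs) lists pulse and blood pressure at Screening, Day 0, "Visit 2-PK (5 min, 10 min, 15 min, 30 min and 1 hours after dosing", then at 24 hours, Day 7, Day 30 and early termination. For each arm and reading, the summary is to be made "using mean values and mean change from baseline values, as well as numbers of subjects with values outside limits of the normal range". The same section adds: "Shift table (normal, abnormal NCS, abnormal CS) will also be provided at each time point by treatment". Subject listings complete the set.

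SAP 6.1 has general rules that also apply. Continuous variables get "mean, standard deviation (SD), median, minimum, and maximum by treatment group". On extra readings it says: "Data from unscheduled visits will not be included in the summary tables but will be included in the listings". SAP 6.2 defines baseline: "the last non-missing assessment prior to first dosing will serve as baseline value". Each subject therefore has an own-baseline change at every reading.

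The reason to look closely at this display is in Protocol 5.2.1: "In 2 GLP cardiovascular studies in dogs, a decrease in blood pressure and an increase in heart rate", among other findings. In monkeys, "a decrease in blood pressure and an increase in heart rate (a compensatory response to decreased blood pressure) were observed", with recovery within a few hours. Protocol 6.1.1 makes safety the primary objective.

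**The concern.** The out-of-range count adds readings above the upper limit to readings below the lower limit. The shift table likewise has one abnormal state, graded by clinical significance and not by direction. A patient who goes from 165 to 125 mmHg after dosing leaves the out-of-range count (if the upper limit lies between those values) and may move from abnormal to normal. If several active-arm patients do this and placebo patients do not, both displays favour the drug while the drug is lowering pressure.

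The animal data point to this effect, and the early readings are placed to catch it. In a trial of about 24 subjects a signal may well take the form of a few individual falls, yet no readable summary counts subjects by the size of their largest fall. Nor does any show how many were still low at 1 hour, the last listed reading before 24 hours.

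**Working it through.** The documents state no blood pressure distribution, normal limits, effect size or SD, so there is no figure of theirs to reproduce. The only documented numerical inputs are 24 subjects at 2:1 (24 × 2/3 = 16 active, 24 × 1/3 = 8 placebo) and five readings from 5 minutes to 1 hour. Everything else below is an assumption.

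**1. The undirected count.** Assume systolic limits of 90 and 140 mmHg, a normal distribution with SD 15, and a uniform fall d from baseline mean m. The expected active-arm count is 16 × [P(X > 140) + P(X < 90)], with X of mean m − d.
- m = 160, no fall: P(X > 140) = Φ(20/15) = 0.909, so 14.5 of 16. With d = 20 the mean sits on the limit, P = 0.50, and the count is 8.0. With d = 30 it is 4.1. Placebo stays at 7.3 of 8.
- m = 150: 12.0 with no fall, 4.1 with d = 20, 1.8 with d = 30.
- m = 125: 2.7 with no fall (2.5 high, 0.2 low). With d = 20 it is still 2.7 (0.2 high, 2.5 low). With d = 30 it rises to 5.9, nearly all low.

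The count therefore moves the wrong way at a raised baseline, stands still at 125 with a 20 mmHg fall, and moves the right way at 125 with a 30 mmHg fall. A high/low split would separate these cases.

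**2. Mean change from baseline.** A uniform 20 mmHg fall appears as −20 against 0, whatever the baseline. For an SD of change s, the standard error of the arm difference is s × √(1/16 + 1/8) = 0.433s. The 95% half-width, 1.96 × 0.433s, is 8.5 mmHg for s = 10 and 12.7 for s = 15. A common 20 mmHg fall would be visible.

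Dilution needs partial response or scattered timing. With fraction p responding, fall d, and the fall spread evenly over k readings, the mean at any one reading is −p × d / k. For p = 0.25 and d = 30 this is −7.5 at a common time (k = 1) and −1.5 if scattered over five readings (k = 5).

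**3. Few responders, scattered timing.** Simulation with baseline mean 155, SD 18 and reading SD 7. A quarter of active subjects fall by 40 mmHg at one random reading and by half that at its neighbours.
- The out-of-range share goes from 78% to 71–73%, about one subject in 16.
- Mean change is −3 to −4 mmHg at each reading.
- A largest fall of 30 mmHg or more occurs in 22% of active subjects, against 0.5% without the effect.

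At the reading with the full fall, responders have mean 155 − 40 = 115 and SD √(18² + 7²) = 19.3. About Φ(25/19.3) = 90% of them are still at or above 90 mmHg. A count of low readings would miss most of them, so the high/low split alone is not enough.

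**4. Minimum and maximum.** In the same simulation, the lowest change in the active arm (16 subjects, five readings) has a median near −49 mmHg, against −20 in placebo (8 subjects). It reaches −30 or lower in 98% of active arms and about 4% of placebo arms. If SAP 6.1's minimum is tabulated for change, the largest single fall shows. The number of subjects who fell does not.

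**The case against.** A reader might infer that the vital-sign tables as a whole dilute or reverse the animal signal, means included. The documents do not support that. Mean change by arm against a concurrent placebo keeps the sign of any fall and the full size of a common one. The scattered one-reading dips that produce dilution are also hard to square with an animal effect that took up to a few hours to recover. If the same quarter of subjects fell by 40 mmHg and stayed down to 1 hour, the mean change there would be 0.25 × −40 = −10 mmHg, not −4.

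A reader might also treat raised baseline pressure, or an effect in humans, as established. Neither is. Only uncontrolled hypertension is excluded, at a redacted threshold (Protocol 8.2), and no baseline pressures are given. The animal doses are redacted. The 12 healthy subjects exposed in the first-in-human study had no clinically significant findings in any safety parameter (Protocol 5.2.2 and 5.3).

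Other cover exists. SAP 6.1 gives minimum and maximum, readings are listed by subject, and Protocol 12.3 requires confirmed, clinically significant readings to be recorded as adverse events. The shift categories are clinical interpretations, so an abrupt fall need not be rated normal. The table shells are a separate document and may say more.

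All of this stands and narrows the point. It does not remove it. Adverse event capture and the shift rating depend on judgement of a value that may now lie within range. Unscheduled repeats stay out of the tables. Minimum and maximum show extremes, not numbers of subjects.

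**Conclusion.** The point holds for two displays. The undirected out-of-range count and the undirected shift table can present a drug-caused pressure fall as improvement if baseline pressure is raised. Under the assumed limits and SD 15, a uniform 20 mmHg fall lowers the expected active-arm count from 14.5 to 8.0 of 16 at a baseline mean of 160, and leaves it at 2.7 at a mean of 125. The result depends on baseline pressure and normal limits that the readable documents do not give. In the few-responder scenario the distortion of the count is only about one subject.

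Mean change by arm is sound for a common fall and weak only for few responders or varied timing. The remaining gap is that no readable summary counts subjects by their largest fall from their own baseline, although the data for it are collected and safety is the primary objective. This is a worthwhile, inexpensive improvement to the display. It does not show that the safety analysis would miss the effect.

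**What to change.** In SAP 10.5:
- Split the out-of-range count, and the abnormal categories of the shift table, into above and below range.
- For the 5-minute to 1-hour readings, add by arm a descriptive table of each subject's largest fall from pre-dose in systolic and diastolic pressure and largest rise in pulse. Include the number of subjects by size of fall and the change still present at 1 hour. Fix the size categories before unblinding and label them as display categories, not clinical limits.

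The cost is one extra table from data already collected, with no change to procedures.

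The downside is noise, since the largest of five readings is more variable than one. With an SD of change of 12 to 15 mmHg and within-subject correlation of 0.5, 16% to 27% of unaffected subjects would show a fall of 20 mmHg or more at some reading. About 8 placebo subjects calibrate this only roughly: 4 of 16 against 0 of 8 gives a two-sided Fisher p of 0.26. The table should therefore be read descriptively, beside the mean change.
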